7.1.2 Part B

The primary objective of this part is to determine the MTD of BI 891065 in combination with BI 754091. To determine the MTD, patients are entered sequentially into escalating dose cohorts. The dose finding will be guided by a Bayesian 5-parameter logistic regression model with overdose control (R15-4233, Chapter 6).

This logistic regression model is defined as follows. Let $\pi_{1,d1}$ be the probability of having a DLT when giving dose d_1 of BI 891065 as monotherapy, and $\pi_{2,d2}$ the probability of having a DLT when giving dose d_2 of the combination partner BI 754091 as monotherapy, respectively. A logistic regression is used to model the dose-toxicity relationship for each of these drugs individually:

$$\text{BI 891065: } \text{logit}(\pi_{1,d1}) = \log(\alpha_1) + \beta_1 \log(d_1/d_1^*)$$

$$\text{BI 754091: } \text{logit}(\pi_{2,d2}) = \log(\alpha_2) + \beta_2 \log(d_2/d_2^*)$$

Here, the doses $d_1^* = 200$ mg and $d_2^* = 3200$ mg represent the reference doses for BI 891065 and BI 754091, respectively.

Assuming no toxicity interaction between the two compounds, the probability of a DLT when giving the combination dose d_1, d_2 is obtained as

$$\pi_{12,d1,d2}^0 = \pi_{1,d1} + \pi_{2,d2} - \pi_{1,d1}\pi_{2,d2}$$

with corresponding odds

$$\text{odds}(\pi_{12,d1,d2}^0) = \pi_{12,d1,d2}^0 / (1 - \pi_{12,d1,d2}^0)$$

In order to account for a potential positive (higher toxicity than expected under independence) or negative (lower toxicity than expected under independence) interaction between BI 891065 and BI 754091, a dose-dependent interaction term $-\infty < \eta < \infty$ is introduced in the model by the following definition:

$$\text{odds}(\pi_{12,d_1,d_2}) = \text{odds}(\pi_{12,d_1,d_2}^0) \exp(\eta \cdot d_1/d_1^* \cdot d_2/d_2^*)$$

and π_{12,d_1,d_2} is used in the likelihood

$$r_{d_1,d_2} \sim \text{Binomial}(n_{d_1,d_2}, \pi_{12,d_1,d_2})$$

where r_{d_1,d_2} denotes the random variable describing the observed number of DLTs in n_{d_1,d_2} patients at the dose combination d_1, d_2 .

Since a Bayesian approach is applied, prior distributions f for each of the parameter vectors $\theta_1 = (\log(\alpha_1), \log(\beta_1))$, $\theta_2 = (\log(\alpha_2), \log(\beta_2))$ and for the interaction term η need to be specified.

The prior distributions for θ_k ($k=1, 2$) will be specified as a mixture of two bivariate normal distributions,

$$f(\theta_k) = a_{1,k} f_1(\theta_k) + a_{2,k} f_2(\theta_k)$$

with

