50 mg q.d.	240 mg	0/6
200 mg q.d.	240 mg	0/8
400 mg q.d.	240 mg	1/5

Table 7.1.2: 6 Posterior probabilities of DLTs

Dose BI 891065	Dose BI 754091	Probability of true DLT rate in			Mean	StD	Quantiles		
		[0,0.16)	[0.16,0.33)	[0.33,1]			2.5 %	50%	97.5%
50 mg q.d.	240 mg	0.977	0.023	0.000	0.071	0.036	0.019	0.065	0.158
200 mg q.d.	240 mg	0.853	0.147	0.000	0.110	0.050	0.035	0.102	0.229
200 mg b.i.d. ^[1]	240 mg	0.708	0.274	0.018	0.132	0.073	0.031	0.118	0.313
400 mg q.d.	240 mg	0.615	0.313	0.072	0.154	0.105	0.02	0.130	0.423

							3		
--	--	--	--	--	--	--	---	--	--

[1] The 200 mg b.i.d. dose is modeled as equivalent to a 300 mg q.d. dose in terms of dose-toxicity relationship in the BLRM.

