Data of the 400 mg cohort of Part A was not completely available by the time of the finalisation of this version of the CTP. Therefore, two possible scenarios of how the prior to be used for Part B could be defined are presented. The first scenario represents the case that none of the patients treated with 400 mg in Part A experiences a DLT. The second scenario represents that case that one of the 6 patients treated with 400 mg in Part A experiences a DLT.

The historical data for BI 891065 can be found in [Table 10.5: 4](#) for Scenario 1 and in [Table 10.5: 5](#) for Scenario 2. [REDACTED]

Table 10.5: 4 Historical data for BI 891065 assuming no DLTs happen at 400 mg (status as of 17 Oct 2018)

Dose	N of patients with DLTs during MTD evaluation period / N of evaluable patients
5 mg	0/2
15 mg	0/1
25 mg	0/3
50 mg	0/4
100 mg	0/3
200 mg	0/3
400 mg	0/6

Table 10.5: 5 Historical data for BI 891065 assuming one patient has a DLT at 400 mg (status as of 17 Oct 2018)

Dose	N of patients with DLTs during MTD evaluation period / N of evaluable patients
5 mg	0/2
15 mg	0/1
25 mg	0/3
50 mg	0/4
100 mg	0/3
200 mg	0/3
400 mg	1/6

The following steps were used to derive the prior distributions for all parameters:

1. θ_1 :
 1. The meta-analytic-predictive prior was derived using the information in [Table 10.5: 4](#) (for Scenario 2 information is in [Table 10.5: 5](#)), allowing for small to moderate between-trial heterogeneity. This mixture component was assigned 90% mixture weight.
 2. A second, weakly-informative component was added with 10% mixture weight.
2. θ_2 :
 1. The meta-analytic-predictive prior was derived using the information in [Table 10.5: 6](#), allowing for moderate to substantial between-trial heterogeneity. This mixture component was assigned 90% mixture weight.
 2. A second, weakly-informative component was added with 10% mixture weight.
3. η : based on the a priori assumption of no interaction between the two compounds, a normal distribution with mean 0 and standard deviation 0.56 was chosen. At the starting dose combination, the corresponding 95% credible interval covers an up to 1.4-fold increase (or decrease) in the odds of a DLT over no interaction.

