The prior distributions for both scenarios are given in [Table 10.5: 7](#) and [Table 10.5: 8](#). The corresponding prior probabilities of a DLT at different dose combinations and the corresponding probabilities of under toxicity, targeted toxicity and over toxicity are shown in [Table 10.5: 9](#) and [Table 10.5: 10](#).

Table 10.5: 7 Prior distributions for Scenario 1 (no DLTs at 400 mg in Part A)

Parameter	means, standard deviations, correlation	mixture weight
$\log(\alpha_1), \log(\beta_1)$: component 1	(-2.404, -0.364), (0.679, 0.737), -0.036	0.9
$\log(\alpha_1), \log(\beta_1)$: component 2	(-2.404, -0.364), (2, 1), 0	0.1
$\log(\alpha_2), \log(\beta_2)$: component 1	(-2.946, -0.193), (0.690, 0.884), -0.037	0.9
$\log(\alpha_2), \log(\beta_2)$: component 2	(-2.946, -0.193), (2, 1), 0	0.1
η	0, 0.56	N/A

Table 10.5: 8 Prior distributions for Scenario 2 (one DLT at 400 mg in Part A)

Parameter	means, standard deviations, correlation	mixture weight
$\log(\alpha_1), \log(\beta_1)$: component 1	(-2.040, -0.093), (0.644, 0.716), -0.095	0.9
$\log(\alpha_1), \log(\beta_1)$: component 2	(-2.040, -0.093), (2, 1), 0	0.1
$\log(\alpha_2), \log(\beta_2)$: component 1	(-2.946, -0.193), (0.690, 0.884), -0.037	0.9
$\log(\alpha_2), \log(\beta_2)$: component 2	(-2.946, -0.193), (2, 1), 0	0.1
η	0, 0.56	N/A

Table 10.5: 9 Prior probabilities of DLTs for Scenario 1 (no DLTs at 400 mg in Part A)

Dose BI 891065	Dose BI 754091	Probability of true DLT rate in			Mean	StD	Quantiles		
		[0,0.16)	[0.16,0.33)	[0.33,1]			2.5%	50%	97.5%
50 mg	240 mg	0.831	0.140	0.030	0.113	0.097	0.023	0.089	0.357
100 mg	240 mg	0.743	0.214	0.043	0.134	0.107	0.029	0.108	0.417
200 mg	240 mg	0.565	0.324	0.110	0.179	0.135	0.032	0.143	0.544
400 mg	240 mg	0.408	0.274	0.318	0.274	0.225	0.018	0.207	0.839

Table 10.5: 10 Prior probabilities of DLTs for Scenario 2 (one DLT at 400 mg in Part A)

Dose BI 891065	Dose BI 754091	Probability of true DLT rate in			Mean	StD	Quantiles		
		[0,0.16)	[0.16,0.33)	[0.33,1]			2.5%	50%	97.5%
50 mg	240 mg	0.804	0.162	0.033	0.118	0.102	0.022	0.093	0.376
100 mg	240 mg	0.684	0.263	0.053	0.147	0.113	0.030	0.119	0.451
200 mg	240 mg	0.450	0.387	0.162	0.211	0.147	0.040	0.174	0.600
400 mg	240 mg	0.297	0.268	0.435	0.342	0.248	0.026	0.282	0.905

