As can be seen from [Table 10.5: 9](#) and [Table 10.5: 10](#), the dose combinations 50 mg BI 891065 and 240 mg BI 754091, 100 mg BI 891065 and 240 mg BI 754091, and 200 mg BI 891065 and 240 mg BI 754091 have prior probabilities of over toxicity below 25% in both scenarios. They fulfill the overdose criterion and are therefore suitable starting dose combinations.

Since prior probabilities for both scenarios shown above are similar, only Scenario 2 with a starting dose combination 100 mg BI 891065 and 240 mg BI 754091 will be used to evaluate the model in terms of performance metrics and data scenarios.

Performance metrics (operating characteristics) illustrate the precision of the design in estimating the MTD under various dose-toxicity relationships through computer simulation. These results are summarized in [Table 10.5: 13](#). In addition, recommendations of the next dose combination by the BLRM with overdose control principle are also provided under various hypothetical outcome scenarios in early cohorts to show how it facilitates on-trial dose-escalation decisions (see [Table 10.5: 11](#)). For simplicity reasons, a cohort size of 3 patients who are all evaluable is assumed.

Hypothetical data scenarios

Hypothetical data scenarios are shown in [Table 10.5: 11](#). These scenarios reflect potential on-study data constellations and related escalation as allowed by the model and the 100% escalation limit. For each scenario, the probability of overdose for the current dose combination, as well as the next potential dose combination and related probabilities of under-dosing, target dose, and over-dosing are shown.

Scenario 1 represents the case that 3 patients are treated at the starting dose combination 100 / 240 and none of these patients experiences a DLT. The model recommendation then is to escalate to the combination 200 / 240. Even if one of these 3 patients experiences a DLT, the model still recommends to escalate to 200 / 240 (see Scenario 2).

Scenario 3 describes a case where de-escalation to 50 / 240 would be required. In case 2 of 3 patients at 100 / 240 experience DLTs, the overdose probability at 100 / 240 exceeds 25%, which implies that 100 / 240 cannot be tested without further data at lower dose levels.

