Scenarios 4 and 5 illustrate that when 3 patients have been treated at 100 / 240 without DLT and then additional 3 patients have been treated at 200 / 240 without DLT, the model would still recommend to treat the next patient with 200 / 240. Only in the case 4 or more patients are treated with 200 / 240 without experiencing a DLT, the model recommends to escalate to 400 / 240. Scenarios 9 and 10 show that in case one patient experiences a DLT at 200 / 240, the model requires 9 additional patients without DLT to allow escalating to 400 / 240.

Scenarios 11 and 12 illustrate possible ways to declare 400 / 240 as the MTD.

Table 10.5: 11 Hypothetical data scenarios

Scenario	Dose [combination] (mg)	# Patients	# DLT	Current Dose [combination]: P (OD)	Next recommended dose [combination]	Next dose [combination]:		
						P (UD)	P (TD)	P (OD)
1	100 / 240	3	0	0.012	200 / 240	0.548	0.369	0.083
2	100 / 240	3	1	0.066	200 / 240	0.335	0.453	0.212
3	100 / 240	3	2	0.256	50 / 240	0.444	0.381	0.175
4	100 / 240	3	0	0.027	200 / 240	0.691	0.282	0.027
	200 / 240	3	0					
5	100 / 240	3	0	0.021	400 / 240	0.488	0.277	0.234
	200 / 240	4	0					
6	100 / 240	3	0	0.117	200 / 240	0.420	0.463	0.117
	200 / 240	3	1					
7	100 / 240	3	0	0.308	100 / 240	0.534	0.412	0.054
	200 / 240	3	2					
8	100 / 240	3	0	0.048	200 / 240	0.547	0.405	0.048
	200 / 240	6	1					
9	100 / 240	3	0	0.014	400 / 240	0.434	0.318	0.249
	200 / 240	10	1					
10	100 / 240	3	0	0.017	400 / 240	0.819	0.164	0.017
	200 / 240	4	0					
	400 / 240	6	0					
11	100 / 240	3	0	0.101	400 / 240	0.522	0.377	0.101
	200 / 240	4	0					
	400 / 240	6	1					
12	100 / 240	3	0	0.107	400 / 240	0.488	0.405	0.107
	200 / 240	10	1					
	400 / 240	6	1					

Operating characteristics

Operating characteristics are a way to assess the long-run behaviour of a model by illustrating the precision of the design in estimating the MTD. Under an assumed true dose-toxicity curve, metrics such as the probability of recommending a dose combination with true DLT rate in the target interval can be approximated via simulation. [Table 10.5: 12](#) describes 4 assumed

true dose-toxicity scenarios that were used to assess the operating characteristics of the model. These scenarios reflect a wide range of possible cases as follows:

- Scenario 1: aligned with prior means
- Scenario 2: high-toxicity scenario
- Scenario 3: low-toxicity scenario
- Scenario 4: non-logistic dose-toxicity scenario

Table 10.5: 12 Assumed true dose-toxicity scenarios

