7.4 PRIMARY ENDPOINT(S)

Part A:

The primary endpoints of Part A are the MTD of BI 891065 and the number of patients with DLTs in the first treatment cycle. The number of patients with DLTs at each dose level will be presented for the first cycle for the MTD evaluation set and for the whole on-treatment period for the treated set separately.

The MTD will be determined by the SRC using recommendations from a Bayesian logistic regression model (BLRM, see CTP Section 7 for details on the model and on the prior). BLRM evaluations for the CTR will be performed once using the number of patients with DLTs during the first cycle from the MTD evaluation set and once using the number of patients with DLTs during the whole on-treatment period from the treated set.

Tables and bar charts displaying the posterior probabilities of the true DLT rates being in either the underdosing interval, the targeted toxicity interval or the over toxicity interval will be produced.

Part B:

The primary endpoints of Part B are the MTD of BI 891065 in combination with BI 754091 and the number of patients with DLTs in the first treatment cycle. The number of patients

with DLTs at each dose level will be presented for the first cycle for the MTD evaluation set and for the whole on-treatment period for the treated set separately.

The MTD will be determined by the SRC using recommendations from a BLRM (see CTP Section 7 for details on the model, the prior for Part B is described in [Section 9.1](#) of this TSAP). BLRM evaluations for the CTR will be performed once using the number of patients with DLTs during the first cycle from the MTD evaluation set and once using the number of patients with DLTs during the whole on-treatment period from the treated set.

Tables and bar charts (per dose level of BI 754091) displaying the posterior probabilities of the true DLT rates being in either the underdosing interval, the targeted toxicity interval or the over toxicity interval will be produced.

Part C:

The primary endpoint of Part C is OR by investigator's assessment based on RECIST v1.1. OR will be analysed descriptively for the treated set in terms of objective response rate (ORR), defined as the proportion of patients with best overall response of CR or PR.

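### The stated BI 754091 reference dose of 3200 mg does not belong to the printed Part B priors, which reproduce the protocol's own tables only with about 240 mg

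*Protocol*

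**What the plan says.** Protocol Section 7.1.2 models each drug with a logistic curve in log(dose/reference dose). It combines the two under independence and multiplies the odds by an interaction factor that depends on both scaled doses. The scaling constants are given as "Here, the doses $d_1^* = 200$ mg and" "d_2^* = 3200$ mg represent the reference doses for BI 891065 and BI 754091, respectively". The BI 754091 constant therefore enters twice: in that drug's logit and in the interaction exponent.

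Appendix 10.5 refers back to Section 7.1.2 for the model and gives no other reference dose. It prints:

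- two possible sets of priors (Tables 10.5: 7 and 10.5: 8);
- the prior DLT probabilities that follow (Tables 10.5: 9 and 10.5: 10);
- twelve data scenarios with the model's recommendation (Table 10.5: 11).

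On Scenario 3 the text says "In case 2 of 3 patients at 100 / 240 experience DLTs, the overdose probability at 100 / 240 exceeds 25" per cent. On Scenario 4 it says "the model would still recommend to treat the next patient with 200 / 240". On the interaction prior it says "At the starting dose combination, the corresponding 95% credible interval covers an up to 1.4-fold increase (or decrease) in the odds of a DLT".

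SAP Section 7.4 states "The MTD will be determined by the SRC using recommendations from a BLRM (see CTP Section 7 for details on the model". The same parenthesis places the Part B prior in TSAP Section 9.1, which is not in the public file.

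**The concern.** A reference dose and the priors on the intercept, slope and interaction are a matched set. The intercept is the log-odds of a DLT at the reference dose, so the same prior means something different when that dose changes. At 240 mg of BI 754091, a 3200 mg reference makes the scaled dose 0.075; a 240 mg reference makes it 1. The first shrinks both the BI 754091 contribution and the interaction almost to nothing.

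This model decides which combinations meet the overdose criterion, and it supports the Part B primary endpoint, the MTD. SAP Section 7.4 also requires it to be run twice for the trial report. An analyst who pairs the stated constant with the printed priors would understate overdose risk and could not reproduce the appendix.

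**Working it through.** **Inputs.** `d1*` = 200 mg and `d2*` = 3200 mg (Section 7.1.2). From Tables 10.5: 7 and 10.5: 8, with weight 0.9 on component 1:

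- BI 891065, Scenario 1: means (-2.404, -0.364), SDs (0.679, 0.737), correlation -0.036.
- BI 891065, Scenario 2: means (-2.040, -0.093), SDs (0.644, 0.716), correlation -0.095.
- BI 754091, both scenarios: means (-2.946, -0.193), SDs (0.690, 0.884), correlation -0.037.
- Component 2 (weight 0.1): same means, SDs (2, 1), correlation 0.
- Interaction: eta normal with mean 0, SD 0.56.

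**Model.**

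`logit(pi_k) = log(alpha_k) + beta_k * log(d_k/d_k*)`

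`pi0 = pi1 + pi2 - pi1*pi2`

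`odds(pi12) = odds(pi0) * exp(eta * d1/d1* * d2/d2*)`

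**Hand check at the prior centre, Scenario 1, 50/240 mg, eta = 0.**

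- BI 891065: -2.404 + exp(-0.364) × log(50/200) = -3.367, so pi1 = 0.033.
- BI 754091 with `d2*` = 240: logit = -2.946, so pi2 = 0.050. Combined: 0.033 + 0.050 - 0.002 = 0.082 (unrounded inputs).
- BI 754091 with `d2*` = 3200: -2.946 + exp(-0.193) × log(0.075) = -5.08, so pi2 = 0.006. Combined: 0.039.

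The printed median is 0.089. Plugging in prior centres only approximates a median, but 240 is close and 3200 is less than half.

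**Full check.** Three million draws from the printed priors, changing only `d2*`, compared with all 64 figures in Tables 10.5: 9 and 10.5: 10:

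| `d2*` (mg) | RMS error |
|---|---|
| 160 | 0.083 |
| 200 | 0.030 |
| 220 | 0.012 |
| **240** | **0.003** |
| 260 | 0.013 |
| 300 | 0.029 |
| 400 | 0.052 |
| 800 | 0.082 |
| **3200 (stated)** | **0.102** |

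The largest single gap is 0.011 at 240 and about 0.23 at 3200.

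Prior probability that the DLT rate is 0.33 or more, at 50 / 100 / 200 / 400 mg BI 891065 with 240 mg BI 754091:

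| | Scenario 1 | Scenario 2 |
|---|---|---|
| Printed | .030 / .043 / .110 / .318 | .033 / .053 / .162 / .435 |
| `d2*` = 240 | .028 / .041 / .107 / .321 | .032 / .051 / .159 / .436 |
| `d2*` = 3200 | .013 / .018 / .031 / .133 | .015 / .022 / .051 / .276 |

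Other ways of keeping 3200 fail. With 3200 in the logit and 240 in the interaction, the largest gap is 0.175 (Scenario 1) and 0.171 (Scenario 2). With the two values swapped it is 0.190 and 0.212. Removing eta, or moving `d1*` to 50, 100, 150 or 400 mg with `d2*` at 3200, still leaves gaps above 0.10. Both terms need about 240.

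**Table 10.5: 11.** Posteriors were computed under the Scenario 2 prior, as the appendix specifies. The rule was the highest target probability among doses with overdose probability below 0.25 and no more than double the current dose. With 240, all 12 recommendations are reproduced and the listed probabilities agree within about 0.014. With 3200, 9 of 12 are. The three that change:

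| Scenario | Data (DLTs/patients) | Printed | With 3200 |
|---|---|---|---|
| 3 | 2/3 at 100 | overdose at 100 is 0.256; go to 50 | 0.222; stay at 100 |
| 4 | 0/3 at 100, 0/3 at 200 | stay at 200 (400 has overdose 0.264 with `d2*` = 240) | 400 has 0.197; go to 400 |
| 7 | 0/3 at 100, 2/3 at 200 | overdose at 200 is 0.308; go to 100 | 0.126; stay at 200 |

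**Interaction sentence.** The upper 95% limit on the odds multiplier is `exp(1.96 * 0.56 * (d1/200) * (240/d2*))`:

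- `d2*` = 240: 1.32 at 50/240 and 1.73 at 100/240.
- `d2*` = 3200: 1.02 and 1.04.
- A value of 1.39 needs `d2*` = 200 at 50/240 or 400 at 100/240. Neither reproduces the tables (errors 0.030 and 0.052).

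**The case against.** The mismatch itself is hard to dispute. The stronger case is that it may not reach the running model.

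- **Prior source.** The SAP takes the Part B prior from TSAP Section 9.1, which cannot be seen and may carry matching priors or its own reference dose. The appendix offers its priors as possible scenarios, written before the 400 mg monotherapy data were complete, and Section 7.1.2 now draws on later data. Priors derived on a 3200 mg scale would be coherent with 3200. This stands: the check shows that Section 7.1.2 and the appendix disagree, not that the code is wrong.
- **No decision has been shown to change.** With the Part B data to date (0/6, 0/8, 1/5 at 50, 200 and 400 mg) and the Scenario 1 prior, overdose at 400/240 is 0.073 with 240 and 0.039 with 3200 (printed in Table 7.1.2: 6: 0.072). At the 300 mg equivalent of 200 mg b.i.d. it is 0.014 and 0.004 (printed 0.018). The reversed scenarios all start at 100/240, a combination absent from Table 7.1.2: 5. SRC review, the 100% escalation cap and the Part A ceiling also apply. This stands too.
- **Limits of the match.** The prior behind Table 7.1.2: 6 is not printed, and agreement there is only approximate: target probability at 200/240 is 0.117 with 240 and 0.046 with 3200, against 0.147 printed. Scenario 9 sits on the limit (printed 0.249; runs at 240 give 0.249 to 0.250), so that match depends on simulation error. Table 10.5: 13 was not reproduced and carries no weight here.

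None of this supports 3200 as the constant for the printed priors.

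**Conclusion.** The concern holds. The constant in Section 7.1.2 and the priors in Appendix 10.5 are not a matched pair. Two separate sets of printed results, the prior tables and the data scenarios, agree with about 240 mg and reject 3200 mg by far more than rounding or simulation error. Read literally, the text errs in the less cautious direction: prior overdose at 400/240 in Scenario 1 falls from 0.318 to 0.133, across the 0.25 limit, and three of 12 model recommendations become less cautious.

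The conclusion rests on the printed priors and the model exactly as Section 7.1.2 writes it. It does not establish which constant the trial code used; the agreement of the tables with 240 suggests a text-only error. It should be corrected in any case, because the SAP names CTP Section 7 as the model source for the Part B MTD. The 1.4-fold sentence is a separate inconsistency that favours neither value.

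**What to change.** 1. Check the BLRM code for the BI 754091 reference dose actually used.
2. State that value in Protocol Section 7.1.2 and in the TSAP model and prior description, next to the priors that belong to it. The tables point to 240 mg, meant here purely as a scaling constant in the model and not as a dosing instruction.
3. If the code does use 3200 mg, re-derive the BI 754091 and interaction priors on that scale and re-issue Tables 10.5: 7 to 10.5: 13 and Table 7.1.2: 6.
4. In either case correct the 1.4-fold sentence and name the starting combination it refers to.

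The cost is one code check, one constant and one sentence, with no patients and no procedures. Tables need re-issuing only under step 3.
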